**Ho:  $CCS_{coflex+decomp.} - CCS_{decomp} \leq 0$  (not superior)**

**Ha:  $CCS_{coflex+decomp.} - CCS_{decomp} > 0$  (superior)**

An informative prior based on IDE study results for the coflex® group will be used. A non-informative will be used for decompression alone. The Bayesian posterior probability that  $(CCS_{coflex+decomp.} - CCS_{decomp}) > 0$  will be determined. **If the posterior probability is  $\geq 0.95$ , superiority will be concluded.**

**Objective 2: (2-year non-inferiority)** This objective is to compare clinical status of patients implanted with the coflex® device in conjunction with surgical decompression relative to surgical decompression alone at two years post operatively by confirming clinical non-inferiority in terms of Month 24 composite clinical success (CCS) defined similarly to the IDE study endpoint. To meet this objective, the following hypotheses will be tested:

**Ho:  $CCS_{coflex+decomp.} - CCS_{decomp} \leq -0.10$  (inferior)**

**Ha:  $CCS_{coflex+decomp.} - CCS_{decomp} > -0.10$  (not inferior)**

These hypotheses will be tested by evaluating the Bayesian posterior probability that the treatment group difference in the likelihood of achieving Month 24 CCS is larger than -0.10, i.e., that the probability of achieving Month 24 CCS for patients implanted with coflex® is no more than 0.10 less than for decompression alone. The IDE Study results will form the basis of an informative prior distribution for the likelihood of success in the group implanted with coflex®. A non-informative will be used for decompression alone. Non-inferiority will be concluded if the posterior probability is at least equal to 0.95.

**Objective 3: (2-year superiority)** If non-inferiority is demonstrated, then the evidence supporting superiority at two-years will be evaluated. This will be done by determining the Bayesian posterior probability that  $(CCS_{coflex+decomp.} -$

	
<math>CCS_{decomp}) > 0</math>. Superiority will be concluded if the posterior probability is at least equal to 0.95.
 
Objective 4: (real conditions of use): The following hypotheses will be tested in order to evaluate whether or not coflex® device performance is clinically inferior in the PAS population compared to the IDE population using a non-inferiority <math>\delta=-0.1175</math>. The following hypotheses will be tested.
 
Ho: <math>CCS_{PAS} \leq CCS_{IDE} - 0.1175</math>
 
Ha: <math>CCS_{PAS} > CCS_{IDE} - 0.1175</math>.
 
Non-inferiority of coflex performance in the PAS population will be concluded if the posterior probability that (<math>CCS_{PAS} > CCS_{IDE} - 0.1175</math>) is at least 0.95.
 
Sample Size Analysis Details concerning the Bayesian simulations for this study were previously reviewed and are included in Bayesian Simulations Memo, Version 4.1, May 5, 2015.
 
Objective 1: (5-year superiority) These Simulations were used to evaluate the power and type 1 error for determining superiority of coflex® in conjunction with surgical decompression relative to surgical decompression alone at Month 60. For the purpose of these simulations it was assumed that the Month 60 success rate would be 0.57 for coflex®. A posterior probability threshold of at least 0.95 was selected. Power was found to be equal to 83% if the true superiority margin is 12.5%. If the true superiority margin is only 10%, then power to conclude superiority is reduced to 65%. Type 1 error was determined through simulation by assuming that the probabilities of Month 60 success were equal to 0.57 for both device groups. The estimated type 1 error rate is equal to 0.037(SD=0.0011) based on an average of 10 identical simulations with varying randomization seeds.
 
Objective 2: (2-year non-inferiority) Bayesian simulations were performed to evaluate the operating characteristics for testing the Objective 1 hypothesis non-inferiority hypothesis. In the pivotal IDE study, 135 of 204 patients (66.2%) achieved Month 24 CCS. These results were used to define the prior distribution for coflex in conjunction with surgical decompression as beta (135.5, 69.5) since the distribution prior to the IDE trial was specified as beta (0.5, 0.5). This Jeffries non-informative prior was assumed for patients undergoing decompression alone. A non-inferiority margin of -0.10 is specified. Non-inferiority will be concluded if the Bayesian posterior probability that (<math>CCS_{coflex+decomp} - CCS_{decomp}) > -0.10</math> is at least equal to 0.95. When evaluating

--	---

statistical power, it was assumed that the true success rate 0.662 for patients treated with coflex®. However, preliminary results from the German decompression study suggest some an advantage of coflex® over decompression alone. Therefore, when evaluating power, Month 24 CCS for decompression alone was assumed to be at least 2% lower, or 0.642. In contrast, Type 1 error was evaluated by assuming that the coflex® success rate was 0.662 but that the success rate for decompression was 0.10 larger. With N=150 patients per group, power was shown to be 89%; and type 1 error was shown to be 0.042 and 0.052 'prior to the prior' and with the prior engaged, respectively.

**Objective 3: (two-year superiority)** Superiority will be evaluated by determining the Bayesian posterior probability that  $(CCS_{coflex+decomp.} - CCS_{decomp.}) > 0$ . Ho will be rejected in favor of Ha if the Bayesian posterior probability is at least equal to 0.95. The same prior distributions that will be used in Objective 2 will be used in the evaluation this posterior probability. The expected device group difference in Month 24 CCS between coflex® and decompression alone was evaluated based on results from an administrative analysis of the ongoing PAS being conducted in Germany. The device group difference in Month 24 overall success was 12.5% (95% CI -3.5% to 28.4%) based on a simplified CCS that incorporated reoperations, lumber injections, and ODI improvements. Bayesian simulations demonstrate that when assuming the same superiority, with N=150 patients per group will result in 88% statistical power to demonstrate superiority. Type 1 error is controlled at <0.05 'prior to prior' and with prior for coflex® engaged. If the true difference is only 10%, then power is reduced to 73%.

**Objective 4: (real conditions use)**

A design was identified that uses a non-inferiority margin of -0.1175 and a 0.95 posterior probability threshold. This design has an estimated type 1 error that of 0.045 and power of about 80%. Other assumptions include expected success rates 0.662 in both groups when determining power.

**Other Methods:**

An alternative composite endpoint will be evaluated that replaces improvements in ODI with improvements in a walking treadmill test. Secondary continuous effectiveness endpoints will be summarized by treatment group over time and as changes over time with descriptive statistics including means, standard deviations, median, minimum and maximum values. Standardized effect sizes (i.e., standardized mean differences) will be computed to facilitate comparisons across measures. Secondary categorical

	
effectiveness endpoints will be summarized by treatment group over time using counts and percentages.
 
Adverse event rates will be summarized by type of AE and for specific AE per patient using counts and percentages; and by event, summarizing event counts by visit interval over time. Device and procedure related events will be summarized by severity. Events listings will be provided that include details such as relatedness, severity, onset and resolution status will be provided for all events and for relevant subsets of events such as serious events and related events.

--	---

## CLINICAL INVESTIGATION PLAN

### 1. Background Information

The treatment of degenerative spinal stenosis is not adequately appreciated in the literature and prospective controlled clinical studies are lacking.

Non-controlled, retrospective studies have shown very different and inhomogeneous results and allow only limited conclusions regarding clinically occurring lower back pain.

Caputy et al. (1992) found in a five-year follow-up period after decompression (n=88) 27% failures, that showed recurrent neurologies and persisting low back pain. Katz et al. (1996) found in a 7-10 years follow-up period (n=88) 20 patients that had to undergo further surgery. 33% complained about severe back pain and 53% showed a severe limitation of walking distance. A large study in Finland with 438 patients could show retrospectively that 38% of the patients evaluated the result of the surgery after decompression as bad or very bad (Airaksinen et al. 1997). Iguchi published in 2000 a series of 37 patients that were all treated surgically more than 10 years earlier. It could be shown that low back pain was clearly harder to treat than leg pain or walking distance. 44% of the patients evaluated the result as only acceptable to bad.

Until now no guidelines for therapeutic treatment are defined. With isolated decompression the main neurological findings are treated. Accompanying back pain is comparably harder to treat.

The coflex® Interlaminar Technology - manufactured by Paradigm Spine - is intended for use as a permanent implant between the lamina of 1 or 2 lumbar motion segments in the treatment of moderate to severe lumbar spinal stenosis. The device is specifically designed to provide stabilization without fusion in cases of stenosis with or without facet joint hypertrophy, subarticular recess stenosis or foraminal stenosis. It is restricted for use to one or two levels in the region of L1 – L5.

The height of the neuroforamen is maintained and the facet joints will be relieved. By this a further destruction is prevented. Unlike conventional stabilization methods as for example spinal fusion, the function of the segment will be maintained and adjacent structures will be effectively protected. Possible risks, which could occur after implantation of the coflex® Interlaminar Technology are breakage of the implant, displacement of the implant, pain which is caused by the implant, infections, bleedings and hematoma. The benefit of the study lies in the fact that first-time prospective data is raised for potential improvement regarding therapy of lumbar back pain with the treatment of the lumbar spinal stenosis, which, in the future, can lead to an improvement of the therapy.

---

 Katz JN et al., Seven- to 10-year Outcome of Decompressive Surgery for Degenerative Lumbar Spinal Stenosis, Spine: Volume 21(1) 1 January 1996 pp 92-97

 Airaksinen O et al, Surgical outcome of 438 patients treated surgically for lumbar spinal stenosis, Spine 22(19) 1997, pp2278 – 2282

 Iguchi T et al., Minimum 10-Year Outcome of Decompressive Laminectomy for Degenerative Lumbar Spinal Stenosis, SPINE Volume 25, Number 14, pp 1754–1759

For further details, including indications, contraindications and associated risks please see the Product Brochure and instructions for use in the appendix of this document.

## 2. Rationale

The coflex® Interlaminar Technology has been in clinical use for more than 10 years and is CE-certified according to the standards. Prior to US approval, only isolated, retrospective data for the clinical success is available (Samani 2000^5, Kaech et al. 2002)

In a clinical study to support US market approval, three hundred twenty-two randomized patients (215 coflex® and 107 fusions) from 21 sites in the United States were enrolled between 2006-2008. Subjects received laminectomy and coflex® interlaminar stabilization or laminectomy and posterolateral spinal fusion with spinal instrumentation in a 2:1 ratio. Overall device success required a 15-point reduction in ODI, no reoperations, no major device-related adverse events, and no post-operative epidural injections.

In this study, coflex® patients experienced significantly ( $p<0.0001$ ) shorter operative times (mean 98 min vs 153 min), less blood loss (mean 110 cc vs 349 cc), and length of stay (mean 1.9 vs 3.2 days). Among patients with no Treatment Failure (no reop and no lumbar injection), there was a trend towards significantly better improvement in mean ODI scores in the coflex® cohort compared to fusion (Month 24 mean 22.0 vs 26.7,  $p=0.075$ ). Both groups demonstrated significant improvement from baseline in all VAS Back and Leg parameters. Among non-Treatment Failures, coflex® patients experienced greater SF-12 Physical Health outcomes ( $p=0.050$ ) and equivalent Mental Health outcomes. coflex® subjects experienced better Month 24 ZCQ outcomes compared with fusion (Symptom Severity ( $p=0.023$ ); Physical Function ( $p=0.008$ ); Satisfaction ( $p=0.006$ )).

Most importantly, 66.2% of coflex® and 57.7% of fusions achieved the FDA Month 24 composite clinical success (CCS-IDE) criterion. Based on these pivotal IDE trial results, the Bayesian posterior probability that coflex® is clinically non-inferior to fusion ( $\delta=0.10$ ) at Month 24 was determined to be  $>0.999$  using non-informative Jeffries prior distributions for both treatment groups. Similarly, the Bayesian posterior probability of coflex® superiority relative to fusion at Month 24 was 0.928. The overall adverse event rate was similar between the groups. At 2 years fusions exhibited significantly increased angulation ( $p=0.002$ ) and a trend towards increased translation ( $p=0.083$ ) at the superior adjacent level, while coflex® maintained normal operative and adjacent level motion. With this data, the FDA determined coflex® interlaminar stabilization to be a safe and efficacious alternative, with certain advantages over lumbar spinal fusion in the treatment of spinal stenosis and low-grade spondylolisthesis.

This randomized multicenter study generated the following peer-reviewed publications:

- Decompression and coflex interlaminar stabilization compared to decompression and instrumented spinal fusion for spinal stenosis and low-grade degenerative spondylolisthesis: Two-year results from the prospective, randomized, multicenter food and drug administration investigational device exemption trial. Davis RJ, Errico TJ, Bae H, Auerbach JD. Spine (Phila Pa 1976) 38(18): 1529-1539, 2013.

 Samani J, Study of a semi rigid interspinous "U" fixation system, 106 patients over six years, Spinal surgery, Child Orthopaedics, 1707, 2000

 Kaech DL et al., The interspinous "U": new restabilization device for the lumbar spine, Spinal Restabilization Procedures, Chapter 30, 355 – 362, 2002, Elsevier Science

- Can low-grade spondylolisthesis be effectively treated by either coflex interlaminar stabilization or laminectomy and posterior spinal fusion? Two-year clinical and radiographic results from the randomized, prospective, multicenter US investigational device exemption trial. Davis RJ, Auerbach JD, Bae H, Errico TJ. J Neurosurgery Spine 19(2): 174-184, 2013.
- Mitigating adverse event reporting bias in spine surgery. Auerbach JD, McGowan KB, Halevi M, Gerling MC, Sharan AD, Whang PG, Maislin G. The Journal of Bone and Joint Surgery 95(16): 1450-1456, 2013.

### 3. Study Objectives and Endpoints

#### 3.1. Study Objectives

##### **Objective 1:**

The first objective of this trial is to evaluate 5-year clinical status of patients implanted with the coflex® device in conjunction with surgical decompression relative to decompression alone. This objective will be accomplished by a Bayesian test of superiority using Month 60 composite clinical success. The composite primary endpoint for this objective is in three parts:

1. At least a 15 point improvement relative to pretreatment baseline in the Oswestry Disability Index (ODI, range 0-100);
2. No reoperations, revisions, removals, or supplemental fixation at the index level(s);
3. No  $\geq 2$  injections or series of injections for any lumbar level\*\*, or nerve block procedures performed to treat spinal stenosis at any lumbar level(s) or a single injection within 12 months of the 5 year endpoint.

\*\* A series of injections is considered 2-3 injections performed between 24-hour and one week intervals designed to treat a single pain event. Secondary injections performed due to patient demand or recurrence of symptoms following the initial injection are considered separate injections and would constitute a study failure.

Additionally, a sensitivity analysis will be performed with the condition where lumbar injections occurring at any time between surgery and Month 60 will be considered a treatment failure.

A lumbar injection is defined as any deep injection into the spine, typically under image-guidance, of steroids and/or other pharmacologic agents (e.g., facet injections or epidural injections by the transforaminal, interlaminar, or caudal routes). Other types of injections are not treatment failures such as trigger point injections, intramuscular injection for systemic administration of steroids, dry-needling, prolotherapy, or acupuncture, but a sensitivity analysis will be performed including all types of injections.

##### **Objective 2:**

The second objective of this study is to compare clinical status of patients implanted with the coflex® device in conjunction with surgical decompression relative to surgical decompression alone at two years post operatively by confirming clinical non-inferiority in terms of Month 24 composite clinical success (CCS) defined similarly to the IDE study endpoint. This objective will be achieved by conducting a Bayesian test of the null hypothesis that the probability of achieving

Month 24 CCS among patients implanted with the coflex® device in conjunction with surgical decompression is no more than 10% smaller than that for patients undergoing surgical decompression alone. An informative prior distribution for the coflex® group was formulated on the basis of results contained in the coflex® SSED.

For the comparison to decompression, the Month 24 CCS will be slightly modified to include any surgical intervention at index level(s). This is because the decompression only group receives no device. In summary, when comparing coflex® in conjunction with decompression to decompression alone, Month 24 CCS will require:

- No “Treatment Failure” on or before the exact 2-year anniversary of the index surgery. Treatment Failure will include:
  1. No surgical intervention at the index level
  2. No lumbar epidural steroid injection including nerve root blocks and facet blocks at any lumbar level
- At least a 15 point improvement relative to pretreatment baseline in the Oswestry Disability Index (ODI, range 0-100).
- No major device-related adverse event defined as an event simultaneously both ‘Serious’ and ‘Definitely’ on or before the exact surgical two-year anniversary or exact five-year anniversary. In the decompression alone group, since there is no device, this endpoint will be identified as any serious AE that is classified as definitely related to surgery.

**Note:** The IDE study defined this CCS component as severe and definitely-related and not as serious and definitely-related. This has been changed to serious and definitely related for consistency with other spine studies for Objectives 2 and 3 only.

#### **Objective 3:**

If non-inferiority is shown at two-years, to evaluate evidence supporting superiority at two-years in terms of Month 24 CCS using the same informative prior distribution for the coflex group.

#### **Objective 4:**

The fourth objective of this trial is to evaluate coflex® device performance in a ‘real conditions of use’ study and to confirm that coflex® device performance is not clinically inferior in the PAS population compared to the pivotal IDE trial population. The same Month 24 composite clinical success (CCS) endpoint used in the IDE trial will be used in these analyses to facilitate this comparison. If non-inferiority is concluded, the PAS results will be used to update the Bayesian posterior probabilities of that were determined in the IDE trial and documented in the coflex® SSED. The Bayesian posterior probabilities of non-inferiority and superiority relative to the fusion control at the end of the coflex® IDE trial were 0.999362 and 0.927550, respectively. These probabilities will be updated using the new coflex® enrollments into this PAS.

### **3.2. Primary Endpoints**

The identical Month 24 CCS endpoint as was used in the IDE will be used to compare PAS results to IDE study results, and to update the Bayesian posterior probabilities of non-inferiority and superiority relative to fusion. This CCS definition requires no Treatment Failure (i.e., no reoperation, revision, replacement, or supplemental fixation at the index level(s) and no epidural injection at any lumbar level); an ODI improvement  $\geq 15$ ; as well as no new or worsening, persistent neurological deficit; and no major device-related adverse event defined as severe and definitely-related

The CCS endpoints using in Objective 2 and 3 replace severe device-related AEs with serious device-related AEs for greater consistency with other spine studies. The relationship will be evaluated relative to the device and the surgical procedure since controls receive no device. For comparison to decompression alone, any surgical intervention at the index site will imply clinical failure.

Month 60 success for this comparison will require the following items:

- At least a 15 point improvement relative to pretreatment baseline in the Oswestry Disability Index (ODI, range 0-100).
- No reoperations, revisions, removals, or supplemental fixation at the index level(s);
- No  $\geq 2$  injections or series of injections for any lumbar level\*\*, or nerve block procedures performed to treat spinal stenosis at any lumbar level(s); or a single injection within 12 months of the 5 year endpoint.

\*\*A series of injections is considered 2-3 injections performed between 24-hour and one week intervals designed to treat a single pain event. Secondary injections performed due to patient demand or recurrence of symptoms following the initial injection are considered separate injections and would constitute a study failure.

### **3.2.1. Discussion about Month 60 Composite Clinical Success (CCS)**

After careful consideration, handling of lumbar injections will differ between the Month 24 CCS and CCS endpoints determined post Month 24, and in particular, for the primary Month 60 CCS to be used in Objective 1 analyses. As with the IDE study, lumbar injections that occur prior to two years post operatively are defined as Terminal Treatment Failures, Month 24 composite clinical failures and further follow-up is censored when summarizing effectiveness endpoints (i.e., ODI, VAS, ZCQ, treadmill). This is designed to (1) produce a composite endpoint that is sensitive to early device failure and to (2) avoid bias arising from inclusion of clinical data that could be reflecting successful secondary treatment of a failed index treatment. A different approach seems advisable for the Month 60 CCS endpoint for use in this ‘real conditions of use’ study. The goal is to avoid classifying calling transient symptom management as a device failure unless there is subsequent re-operation or unless patient status is compromised as reflected in lack of an ODI improvement from baseline that is less than 15%. Therefore, for Month 60 CCS, lumbar injections occurring within 12 months of the Month 60 visit will indicate Month 60 CCS failure (as well as those within the first 24 months post-surgery). This is because a lumbar injection within 12 months of the Month 60 visit can confound the Month 60 assessment. Similarly, when determining intermediate CCS at Month 36 and Month 48, lumbar injections within 12 months of these clinic visits will indicate CCS failure for that time point, but not necessarily for subsequent time points. However, patients with 2 or more series of injections will be defined at terminal failures, that is, as a CCS failure at that time point and all subsequent timepoints.

As noted above, handling of lumbar injections will differ between the Month 24 CCS and CCS endpoints determined post Month 24, and in particular, for the primary Month 60 CCS to be used in Objective 1 analyses. In sensitivity analysis, lumbar injections occurring at any time between surgery and Month 60 will be considered a treatment failure. All other endpoints in the Month 60 CCS analysis remain identical in the sensitivity analyses.

A lumbar injection is defined as any deep injection into the spine, typically under image-guidance, of steroids and/or other pharmacologic agents (e.g., facet injections or epidural injections by the

transforaminal, interlaminar, or caudal routes). Other types of injections are not treatment failures such as trigger point injections, intramuscular injection for systemic administration of steroids, dry-needling, prolotherapy, or acupuncture.

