### 3.3. Secondary Endpoints

- ODI change compared to baseline at 24 and 60 months as a continuous variables and in terms of achieving at least a 15 point improvement.
- Change in Visual Analog Scale (VAS) for low back pain (on the 100 mm scale) after 24 and 60 months compared to baseline as a continuous variables and in terms of achieving a 20 point improvement.
- Change in right and left leg pain using a Visual Analog Scale (VAS) 100 mm scale after 24 and 60 months compared to baseline as a continuous variable and in terms of achieving a 20 point improvement. A separate analysis will be performed to compare VAS scores for the “worst” legs.
- Change of Zurich Claudication Questionnaire (ZCQ) after 24 and 60 months compared to baseline:
  - Symptom severity (range 1-5)
  - Physical function (range 1-4)
  - Patient satisfaction (range 1-4, no baseline).
  - ZCQ Overall Success ( $\geq 2$  of 3 of the following)
    - Improvement in symptom severity  $\geq 0.5$
    - Improvement in physical function  $\geq 0.5$
    - Satisfied or somewhat satisfied as defined by a score of  $\leq 2.5$  points on the patient satisfaction domain.
  - ZCQ Overall Success components
- Maintenance or improvement in EQ-5D compared to baseline
- Change from baseline to Month 24 and Month 60 in maximum walking time from treadmill test as a continuous variable and in terms of achieving at least an 8 minute improvement or maximum time of 15 minutes.
- Change from baseline to Month 24 and Month 60 in time to symptoms from treadmill test as a continuous variable and in terms of achieving at least an 8 minute improvement or maximum time of 15 minutes.
- Neurological status (no new or worsening, persistent neurological deficit)
- Radiography Endpoints
  - Assessment of significant migration of the implant or the complete expulsion (significant is defined  $> 5$  mm).
  - Assessment of spinous process fracture.
  - Assessment of maintenance of foraminal height
  - Assessment of adjacent level disease determined by independent radiographic review
- Correlation of foraminal height changes to improvement of walking distance on a treadmill (after 24 and 60 months compared to baseline).

 Pratt RK et al., The Reliability of the Shuttle Walking Test, the Swiss Spinal Stenosis Questionnaire, the Oxford Spinal Stenosis Score and the Oswestry Disability Index in the Assessment of Patients with Lumbar Spinal Stenosis. Spine Vol. 27 (1) pp. 84-91.

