### **5.1.2. Secondary Surgical Interventions**

Reoperations, revisions, removals and supplemental fixation are defined as follows:

- A revision is a procedure that adjusts or in any way modifies or removes part of the original implant configuration, with or without replacement of a component. A revision may also include adjusting the position of the original configuration.
- A removal is a procedure where all of the original system configurations are removed with or without replacement.
- A reoperation is any surgical procedure at the involved level(s) that does not remove, modify, or add any components to the system. Note: a surgery to alleviate post-operative superficial wound problems within the immediate post-operative 30 day window will not be considered a treatment failure.
- A supplemental fixation is a spinal procedure in which additional instrumentation not under study in the protocol is implanted (e.g., supplemental placement of a rod/screw system or a plate/screw system) at the index level(s).

If a subject in either study group undergoes a reoperation, revision, removal, or supplemental fixation procedure, the subject should remain in the study and should continue to be followed up within the study. Such patients will be considered a Treatment Failure.

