## 7.2. Analysis Sets

The following analysis sets are defined.

***Intent-to-treat analysis set – Propensity Score Selected (ITT-PS Selected):*** The ITT-PS Selected analysis set will include all subjects assigned to either the study or control groups in which treatment was attempted as defined by the recording of incision time. Subjects will be classified by the group in which they are assigned, regardless of whether or not that treatment was actually completed. Intraoperative failures will be included in primary non-inferiority testing as composite clinical endpoint failures. Primary efficacy analyses will be conducted using the ITT-PS Selected analysis set. A subject must be selected into a PS subclass in order to be included in analyses. The PS subclassification procedure is designed to retain all subjects receiving the study device, if possible. Since selection into a PS subclass is the observational study equivalent to randomization in a randomized study, control subjects not selected into a PS subclass will not be included in the ITT-PS Selected analysis set and not included in primary effectiveness and safety analyses. Safety data will be summarized separately for trimmed controls.

***Completers Analysis Sets:*** Completers analysis sets will be defined at ITT-PS Selected evaluable for composite clinical success.

***Safety analysis set:*** The Safety analysis set will include all subjects in the ITT-PS Selected analysis set plus study device patients who were not selected into a PS subclass, if any. Study device patients who were not selected into a PS subclass will be assigned to the subclass with the largest propensity scores for analyses that control for PS. Primary safety analyses will be conducted using the Safety analysis set.

***Per Protocol analysis set (PP):*** The PP analysis set will include subjects in the ITT-PS Selected analysis set with no major protocol violations of inclusion or exclusion criteria, as determined by the Clinical Events Committee (CEC) and who are evaluable for the Month 24 composite clinical success endpoint (Objective 2, 3, and 4) or evaluable for the Month 60 CCS (Objective 1). It may also exclude subjects with confounding medical events or treatments following index surgery that are expected bias determination of the primary composite clinical success endpoint, as determined by the CEC. Secondary efficacy analyses will be conducted using the PP analysis set.

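### Secondary responder rates are planned among patients without a Treatment Failure, so the arms are compared on a subset selected after surgery, most consequentially for VAS and ZCQ

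*Combined protocol and SAP*

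**What the plan says.** Section 3.2.1 states that "lumbar injections that occur prior to two years post operatively are defined as Terminal Treatment Failures", and continues: "Month 24 composite clinical failures and further follow-up is censored when summarizing effectiveness endpoints (i.e., ODI, VAS, ZCQ, treadmill". One of its reasons is to "avoid bias arising from inclusion of clinical data that could be reflecting successful secondary treatment of a failed index treatment". The only event this sentence names is a lumbar injection.

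Section 5.1.2 deals with reoperation, revision, removal and supplemental fixation. After any of these, "the subject should remain in the study and should continue to be followed up within the study", and "Such patients will be considered a Treatment Failure". It does not say how their later scores enter the secondary tables.

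Section 3.3 sets responder forms of the censored scales at Months 24 and 60: ODI "in terms of achieving at least a 15 point improvement", with corresponding criteria for VAS, ZCQ and treadmill. Section 7.9 reports these as counts and percentages by group and gives no denominator rule. Section 7.2 adds: "Secondary efficacy analyses will be conducted using the PP analysis set". It also lets the Clinical Events Committee (CEC) take out of that set patients whose events or treatments after index surgery are thought to confound the composite.

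**The concern.** The reason given for censoring supports setting aside scores recorded after a rescue. It does not support setting aside the patient. Under the rule as written, a patient injected before two years has no usable later score. With no instruction to count that patient as a non-responder, he or she drops out of the percentage, and the responder rate becomes conditional on something that happens after treatment.

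Treatment is not randomised. Comparability rests on propensity score subclasses formed from baseline covariates in ITT-PS Selected (Sections 7.1 and 7.17.1). Nothing makes the arms comparable among those who later avoid a Treatment Failure. If failure rates differ, the secondary tables can flatter the arm with more failures, and can appear to disagree with the composite for no clinical reason.

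**Working it through.** The plan states no figure for this point, so there is none to reproduce. The check has three parts.

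**1. Which patients are affected**

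- Injection before two years: censoring is written (Section 3.2.1).
- Index-level surgery: censoring is not written. It is a reasonable inference. Section 3.2.1 says it follows the IDE study. Section 2 reports the IDE comparison of mean ODI at Month 24 among patients with neither reoperation nor injection. Section 5.1.1 describes ODI as the status measure for patients without Treatment Failure.
- Month 60: Section 3.2.1 goes on to adopt a different injection rule for the Month 60 CCS, but does not lift the censoring for secondary summaries. Hence apparently, not certainly.
- Visits before the failure stay in.
- PP set: it requires the patient to be evaluable for CCS, and a Treatment Failure is evaluable, as a failure. That condition does not remove these patients; the discretionary CEC exclusion could.

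**2. Size of the effect**

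Let f be an arm's Treatment Failure rate and r the responder rate among its non-failures. The documents give neither by arm, so all values below are assumptions.

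- Rate with failures censored: r
- Rate with failures as non-responders: (1 − f) × r
- Overstatement within one arm: f × r. At r = 75%, this is 0.10 × 0.75 = 7.5 points for f = 10% and 0.30 × 0.75 = 22.5 points for f = 30%.
- With r equal in both arms, the hidden difference is r × (difference in f): from 0.70 × 0.05 = 3.5 points to 0.80 × 0.15 = 12 points.

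| r, coflex / control | f, coflex / control | Difference with failures censored | Rates with failures counted | Difference with failures counted |
|---|---|---|---|---|
| 80% / 80% | 15% / 25% | 0 | 0.85 × 0.80 = 68%; 0.75 × 0.80 = 60% | +8 |
| 75% / 75% | 15% / 25% | 0 | 63.75%; 56.25% | +7.5 |
| 75% / 75% | 20% / 20% | 0 | 60%; 60% | 0 |
| 75% / 75% | 25% / 15% | 0 | 56.25%; 63.75% | −7.5 |
| 80% / 75% | 15% / 25% | +5 | 68%; 56.25% | +11.75 |
| 80% / 75% | 25% / 15% | +5 | 60%; 63.75% | −3.75 |

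The shift can favour either arm and, in the last row, reverses the sign.

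**3. Who remains in the summaries**

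Section 7.7.2 gives an IDE Month 24 CCS of 135/204 = 66.2%. If 10%, 20% or 30% of patients were Treatment Failures (assumed), CCS success among the rest would be 0.662/0.90 = 73.6%, 0.662/0.80 = 82.8% or 0.662/0.70 = 94.6%. About 26%, 17% or 5% of the patients left in the tables would still be CCS failures, for example through too little ODI improvement.

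**The case against.** Five points can be made for the plan as it stands.

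- **The composites already count failures.** The primary CCS combines ODI improvement with absence of Treatment Failure and is analysed in ITT-PS Selected. CCS-WDT (Section 7.8) does the same with the treadmill for Objectives 1 to 3. This stands. For ODI and treadmill the gain is modest. VAS and ZCQ have no specified composite, and the further composites in Section 7.14 are optional.
- **Failure rates will be visible.** Section 7.13 gives Kaplan-Meier curves and life tables by group through 24 months. This helps a careful reader but leaves the responder percentages themselves conditional.
- **The secondary endpoints are descriptive.** Section 7.9 gives intervals only, with no posterior threshold. This stands, and it limits the consequence.
- **The denominator is left unstated rather than wrongly stated.** This is partly right. The censoring, however, is a stated rule, and nothing in Section 7.9 offsets it.
- **The numbers are assumed.** They are. They show what could happen, not what will.

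Two stronger readings are tempting. A reader might infer that the tables contain only patients in whom treatment worked. They do not: a patient with poor scores and no injection or reoperation stays in as a non-responder. A reader might also take the plan to say that a reoperated patient leaves the denominator. The censoring sentence names injections only, and the section on secondary surgery keeps those patients in follow-up without any censoring rule.

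**Conclusion.** The point holds in this limited form. Following the plan as written gives secondary responder rates conditional on no early lumbar injection and, by inference, no index-level reoperation. The arms are not assured of balance in that subset. Under the assumed rates, each arm is overstated by 7.5 to 22.5 points, and a difference of 3.5 to 12 points between arms can be hidden when response among non-failures is equal. The direction cannot be predicted from the documents, and no shift arises if failure and response rates are equal in both arms. No primary conclusion is at risk, because the primary CCS counts these patients as failures. The change is worth making before outcomes are unblinded, chiefly for VAS and ZCQ.

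**What to change.** In Section 7.9, state that the secondary responder endpoints are analysed in ITT-PS Selected, with patients who have had a prior Treatment Failure (lumbar injection or index-level surgery) counted as non-responders at Month 24 and Month 60. Name both events explicitly, so that the handling of reoperated patients no longer rests on inference, and say whether the censoring in Section 3.2.1 extends to Month 60. Keep the censored and PP tables as supportive, which preserves comparison with the IDE study.

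The cost is SAP wording and additional table columns; no new visits or data are needed. The drawback is presentational: responder rates will look lower than in the IDE-style tables.
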